6.2.8.2. Classification of Adverse Events

Adverse events are to be recorded on the AE page of the patient's case report form (CRF). Severity will be graded according to the following definitions:

- **Mild:** The patient experiences awareness of symptoms but these are easily tolerated or managed without specific treatment.
- **Moderate:** The patient experiences discomfort enough to cause interference with usual activity, and/or the condition requires specific treatment.
- **Severe:** The patient is incapacitated with inability to work or do usual activity, and/or the event requires significant treatment measures.

Action taken will be categorized as none, study drug discontinued, dose modified, required concomitant medication, required procedure, or other.

Event outcome at resolution or time of last follow-up will recorded as event resolved, resolved with sequelae, ongoing, or death.

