The results of the video-EEG (including presence or absence of hyperventilation), CGI-I, and seizure diary assessments will be summarized using summary tables, listings, and figures (TLFs), as appropriate. Continuous variables will be summarized using descriptive statistics: sample size (n), mean, standard deviation (SD), or coefficient of variation (CV %) as appropriate, median, interquartile range, minimum and maximum. Categorical variables will be summarized by presenting the number (frequency) and percentage in each category.

Safety Analysis

All safety assessments, including AEs, clinical laboratory evaluations, vital signs, 12-lead ECGs, C-SSRS (children and adolescents aged 7 to 17 years, if appropriate), concomitant AED blood levels, physical and neurological examinations will be listed. When appropriate, they will be summarized with descriptive statistics by age and dose cohort. The Medical Dictionary for Regulatory Activities (MedDRA; Version 20.0 or higher) will be used to classify all adverse events with respect to system organ class and preferred term. Adverse event summaries will include only TEAEs, which will be summarized for each treatment group.

Clinical laboratory findings and vital signs will be summarized for all patients for observed values and change from baseline. Shifts from baseline according to normal range criteria will also be presented for all patients.

The neurological examination results will be listed and summarized descriptively. Shifts from baseline according to normal and abnormal criteria will also be presented for all patients in the safety population.

Results of physical examinations conducted throughout the study will be presented in listings and summarized descriptively. Shifts from baseline according to normal and abnormal criteria will also be presented for all patients in the safety population.

Prior medication and concomitant medications will be reported in the data listings.

Statistical analyses will be performed using SAS® (Version 9.3 or higher, SAS Institute Inc.) or R (Version 3.3 or higher, Roswell Park Cancer Institute).

Pharmacokinetic Analysis

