3.5. Stopping Rules

The investigator reserves the right to terminate the study in the interests of patient safety and welfare. The Sponsor reserves the right to terminate the study at any time for administrative reasons.

Patients will also be discontinued from the study if they meet the following criteria:

- ALT or AST $> 3 \times$ ULN with (or the appearance of) fatigue, nausea, vomiting, right upper quadrant pain or tenderness, fever, rash, and/or eosinophilia $> 5\%$
- ALT or AST $> 8 \times$ ULN
- ALT or AST $> 5 \times$ ULN for more than 2 weeks
- ALT or AST $> 3 \times$ ULN and bilirubin $> 2 \times$ ULN or INR > 1.5

For patients meeting the above criteria, the investigator will arrange for the patient to return to the investigational site as soon as possible (within 24 hours of notice of abnormal results) for repeat assessment of ALT, AST, bilirubin, and alkaline phosphatase (ALP), detailed history, and physical examination. Patients will be followed until all abnormalities have normalized (in the investigator's opinion) or returned to the baseline state. If the patient is unable to return to the investigational site, repeat assessments may be performed at a local laboratory.

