6.2.8. Adverse Events and Serious Adverse Events

6.2.8.1. Definition of Adverse Events

An AE is defined as any untoward medical occurrence in a patient administered a pharmaceutical product during the course of a clinical investigation. An AE can therefore be any unfavorable and unintended sign, symptom, or disease temporally associated with the use of an investigational product, whether or not thought to be related to the investigational product.

Patients will be monitored throughout the study for AEs. Monitoring for treatment-emergent AEs will begin as soon as the patient is dosed. All AEs must be followed until they are resolved or stabilized, or until all attempts to determine resolution of the event are exhausted. The investigator should use their discretion in ordering additional tests as necessary to monitor the progress of such events.

An AE may be:

- A new illness, not documented in the patient's medical history;
- Worsening of a concomitant illness;
- An effect of the study medication; it could be an abnormal laboratory value, as well as a significant shift from baseline within normal range which the qualified investigator or medical qualified designate considers to be clinically important;
- A combination of two or more of these factors.

Surgical procedures themselves are not AEs. They are therapeutic measures for conditions that required surgery. The condition for which the surgery is required is an AE, if it occurs or is detected during the study period. Planned surgical measures permitted by the clinical study protocol and the conditions(s) leading to these measures are not AEs, if the condition(s) was (were) known before the start of study treatment. In the latter case, the condition should be reported as medical history.

Absence seizures will not be considered AEs. However, new seizure types and injury resulting from a seizure will be captured as AEs.

Patients will be monitored throughout the study for AEs. All AEs must be followed until they are resolved or stabilized, or until all attempts to determine resolution of the event are exhausted. The investigator should use his/her discretion in ordering additional tests as necessary to monitor the progress of such events.

Adverse events reported prior to dose administration will be recorded as part of the patient's medical history.

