Previous clinical trial experience has shown that somnolence, diarrhea, and transaminase elevations may be associated with CBD treatment. Therefore, Insys Development Company has identified these as Adverse Events of Special Interest.

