8.2. Safety Endpoints

Changes in safety endpoints will be reported as mean/median change from baseline at relevant time points and as a listing of events that fall outside normal limits.

- Incidence, type, and severity of AEs and serious adverse events (SAEs) occurring during the Treatment Period (i.e., treatment-emergent AEs [TEAEs]).
- Changes from Baseline (Visit 2) in vital signs during the Treatment Period.
- Changes from Screening in laboratory values (hematology, chemistry, and urinalysis) during the Treatment Period.

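### The AE severity scale has no laboratory criterion, so a symptom-free transaminase rise, an AE of special interest, fits no grade or defaults to mild

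*Protocol*

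**What the plan says.** - **Scale.** Section 6.2.8.2 sets one scale for all events: "Severity will be graded according to the following definitions". Mild reads "The patient experiences awareness of symptoms but these are easily tolerated or managed without specific treatment". Moderate reads "The patient experiences discomfort enough to cause interference with usual activity, and/or the condition requires specific treatment". Severe needs incapacity or significant treatment measures. No multiple of ULN or other laboratory criterion for severity appears here or elsewhere in the protocol.
- **Laboratory events.** Section 6.2.8.1 allows an abnormal laboratory value to be an adverse event. It also states that "somnolence, diarrhea, and transaminase elevations may be associated with CBD treatment" and designates these three as events of special interest.
- **Stopping.** Section 3.5 introduces four liver criteria with "Patients will also be discontinued from the study if they meet the following criteria". One of them is ALT or AST above 8 x ULN, with no other condition.
- **Reporting.** Section 8.2 lists as a safety endpoint "Incidence, type, and severity of AEs and serious adverse events (SAEs) occurring during the Treatment Period". Section 8.6.4.1 plans event summaries for each treatment group, including one by severity, and a separate summary of events that lead to discontinuation.

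**The concern.** The protocol requires the investigator to give every adverse event an intensity rating (6.2.8.7). For one of its three events of special interest, the scale cannot register the feature that matters, the size of the laboratory value. Two children with the same ALT could be graded differently at different sites, and two with very different ALT values could be graded alike.

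This is a dose-finding trial whose secondary objectives include safety and tolerability, and it is open-label at about 8 sites. It permits stable valproate, for which the protocol itself mentions liver failure as a potential side effect (section 1.4). The hepatic profile by dose is therefore something readers will look for, and severity by treatment group is one of the tables they will use.

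The gap cannot be left to the analysis plan. The grade is assigned on the case report form during the trial, under the protocol's definition. Later tables of laboratory values can supplement grades collected inconsistently, but cannot repair them.

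**Working it through.** There is no stated figure to reproduce. The check applies the definitions in 6.2.8.2 to events that meet the criteria in 3.5.

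**Step 1. Which liver criteria can be met without symptoms?**

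| Criterion in 3.5 | Symptom needed? |
|---|---|
| ALT or AST > 3 x ULN with a listed symptom or sign, and/or eosinophilia > 5% | Not strictly: the and/or lets eosinophilia alone suffice |
| ALT or AST > 8 x ULN | No |
| ALT or AST > 5 x ULN for more than 2 weeks | No |
| ALT or AST > 3 x ULN with bilirubin > 2 x ULN or INR > 1.5 | No |

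Three of the four need no symptom, and the first can also be met without one.

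**Step 2. Grade a symptom-free child above 8 x ULN.**

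- *Severe*: no incapacity and no significant treatment measure, so not met.
- *Moderate*: no discomfort and no specific treatment, so not met unless stopping the drug counts as treatment. The protocol separates the two. In 6.2.8.2, discontinuing study drug is a different action from concomitant medication or a procedure, and in 6.2.8.5 treatment and drug withdrawal are separate actions for serious events.
- *Mild*: requires that the patient be aware of symptoms, so not literally met.

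Read strictly, the event has no grade. In practice the lowest grade is the likely default. The result is the same for a symptom-free value at any other multiple of ULN, because size enters none of the definitions.

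**Step 3. Which events depend on the severity grade?** An elevation above 8 x ULN that leads to withdrawal appears in the separate discontinuation summary. Symptom-free elevations between 3 and 8 x ULN need not. The duration rule at 5 x ULN seldom changes this. On-treatment chemistry is scheduled at Visit 3 (Day 1), Visit 4 (end of Week 2, about Day 14) and Visit 6 (Week 4, Day 7, that is Day 28). The gap from Visit 4 to Visit 6 is 28 - 14 = 14 days, or 11 to 17 days with the Visit 6 window of ±3 days. A rise first seen at Visit 4 can thus be confirmed by scheduled tests as lasting more than 2 weeks only at the end of treatment, if at all. A rise first seen at Visit 6 cannot be confirmed during treatment.

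**Step 4. Weight of one child.** 1/10 = 10 percentage points in a cohort.

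**The case against.** The strongest reply is that only one output is affected. Events causing discontinuation are summarized separately (8.6.4.1). The action taken is recorded apart from severity (6.2.8.2). A medically significant event can qualify as serious without symptoms (6.2.8.4). Chemistry values get descriptive statistics (8.6.4.2), and out-of-range findings are listed (8.2). With 10 children per cohort, a very high value will be seen. The study is exploratory, with no inferential safety analysis. All of this stands, and it confines the point to the severity summary. It does not fill the gap for symptom-free elevations that do not stop treatment. The shift display, "Shifts from baseline according to normal range criteria will also be presented for all patients", does not separate a value just above normal from one many times higher, and the serious-event route rests on judgement.

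A reader might infer more than the text supports:

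- *That such an event is mild by definition.* Mild itself requires symptoms, so this is only a likely default. An investigator who counts withdrawal and urgent re-testing as treatment measures could grade higher.
- *That the severity table would show, say, 0/10 instead of 2/10 moderate or severe events.* No passage ties a multiple of ULN to a grade, so no misclassification count can be derived.
- *That 3.5 and 6.2.8.2 flatly contradict each other.* Severity, seriousness and action taken are separate attributes, so an event of low intensity may lead to withdrawal. The defect is a missing criterion.
- *That recording any elevation is left to the investigator's judgement.* The clause "which the qualified investigator or medical qualified designate considers to be clinically important" follows the words on shifts within the normal range and may govern only those.
- *That 8.2 promises severity by dose.* The grouping comes from 8.6.4.1.

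**Conclusion.** The point holds in this form: the severity scale cannot grade a symptom-free transaminase elevation by its size, and the grade is either undefined or probably mild, even when a symptom-free discontinuation criterion in 3.5 is met. The summary of events by severity and treatment group is unreliable for this event of special interest, chiefly for elevations that do not lead to discontinuation.

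The size is bounded but not estimable. Each affected child carries 10 percentage points in a cohort of 10, and the documents give no expected number of such children. The conclusion assumes that stopping the drug is not itself treatment, as the protocol's own action categories suggest, and that default to the lowest grade is likely but not certain. If investigators read the scale differently, the consequence is inconsistent grades between sites, and the table is no more dependable. The correction is worth making, but the documents do not support a claim that hepatic events would be concealed.

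**What to change.** Add to 6.2.8.2 that transaminase events are graded from the peak laboratory value in multiples of ULN. Map each range explicitly to mild, moderate or severe, and reconcile the mapping with the levels already used in 3.5. Those levels are composite stopping criteria, some with a duration or a second finding attached, so they cannot serve as a severity scale until the sponsor states which range carries which grade. No stopping threshold changes.

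As a supporting output, the number of children per cohort whose peak post-dose ALT or AST exceeds 3, 5 and 8 x ULN can be shown beside the investigator-reported events. This table could equally sit in the statistical analysis plan, and its absence from the protocol is not a fault.

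The cost is a short grading rule with its mapping, a matching instruction for the case report form, and one table from data already collected. The downside is that some events move to a less favourable grade.

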6.2.8.3. Causality/Drug Relationship Assessment

The relationship of the event to the study drug should be determined by the investigator according to the following criteria:

- **Definitely related:** The event follows a reasonable temporal sequence from the time of drug administration that cannot be explained, follows a known or expected response pattern to the study drug, that is confirmed by improvement on stopping and reappearance of the event on repeated exposure and that could not be reasonably explained by other factors such as the patient's clinical condition, intercurrent illness, or concomitant drugs.
- **Not related:** The event is most likely produced by other factors such as the patient's clinical condition, intercurrent illness, or concomitant drugs, and does not follow a known response pattern to the study drug, or the temporal relationship of the event to study drug administration makes a causal relationship unlikely.
- **Possibly related:** The event follows a reasonable temporal sequence from the time of drug administration, and/or follows a known response pattern to the study drug, but could have been produced by other factors such as the patient's clinical condition, intercurrent illness, or concomitant drugs.
- **Unlikely related:** The event follows little or no temporal sequence from the time of drug administration that makes a causal relationship improbable and/or other factors such as the patient's clinical condition, intercurrent illness, or concomitant drugs is a more likely alternative.
- **Probably related:** The event follows a reasonable temporal sequence from the time of drug administration, and/or follows a known response pattern to the study drug, and cannot be reasonably explained by other factors such as the patient's clinical condition, intercurrent illness, or concomitant drugs.

6.2.8.4. Definition of Serious Adverse Events

A serious AE (SAE) is any AE that fulfills any of the following criteria, as per 21 CFR 312.32:

- Results in death;
- Is life-threatening;
- Requires in-patient hospitalization or prolongation of existing hospitalization;
- Results in persistent or significant disability or incapacity;
- Is a congenital anomaly or birth defect;
- Is medically significant or requires intervention to prevent one of the outcomes listed above.

Serious AEs will be captured from the time of consent through the end of the study.

6.2.8.5. Serious Adverse Events Actions Taken

Actions taken may consist of:

- None: No action taken
- Treatment: Standard of care measures instituted
- Drug withdrawn: Study medication was permanently discontinued because of the AE
- Unknown: Not known, not observed, not recorded, or refused

6.2.8.6. Serious Adverse Events Outcome at the Time of Last Observation

The outcome at the time of last observation will be classified as:

- Recovered/resolved
- Recovered/resolved with sequelae
- Not recovered/not resolved
- Death
- Unknown

6.2.8.7. Adverse Event Recording and Reporting

Adverse events will be recorded throughout the study in the source documents and in the CRFs. The investigator will rate AEs for seriousness, intensity, causality, action taken, and outcome as described in the previous section.

Expedited reporting is required for serious unexpected adverse drug reactions. Fatal or life-threatening unexpected drug reactions must be reported by the Sponsor to regulatory agencies no more than 7 days after the Sponsor's first knowledge of the reaction; followed by as complete a report as possible within 8 additional days. Unexpected drug reactions must be reported no later than 15 days after the Sponsor's first knowledge of the reaction. In order to comply with these requirements, the investigator or delegate must inform the Sponsor immediately upon occurrence of any SAE. The site will complete the SAE Report Form as

thoroughly as possible and e-mail it to Insys within 24 hours of the investigators first knowledge of the event.

Sponsor contact information is listed below:

PPD

Director of Pharmacovigilance
Insys Development Company, Inc.
Email: [contact]

These SAE reports must contain the following information:

- A. Study name/number
- B. Study drug
- C. Investigator details (name, phone, fax, e-mail)
- D. Patient number
- E. Patient initials
- F. Patient demographics
- G. Clinical event
 - 1) Description
 - 2) Date of onset
 - 3) Treatment (drug, dose, dosage form)
 - 4) Adverse event relationship to study drug
 - 5) Action taken regarding study drug in direct relationship to the AE
- H. If the AE was fatal or life-threatening
- I. Cause of death (whether or not the death was related to study drug)
- J. Autopsy findings (if available)

The Sponsor or its representative will be responsible for notification to regulatory agencies.

6.2.8.8. Adverse Event Follow-Up

All non-serious AEs that are not related or unlikely to be related to study treatment will be followed until the end of study participation. All SAEs or AEs that are considered as possibly, probably, or definitely related to treatment will be followed until resolution or stabilization.

6.2.8.9. Safety Data Review

Available safety data will be reviewed on an ongoing basis to ensure doses are generally well tolerated. Details of the safety data review will be provided in the Data Monitoring Charter.

6.2.8.10. Special Considerations

Cannabidiol inhibits drug metabolism mediated by a subset of CYP proteins (see Section [Section 1.1.2](#)). Thus, the investigator and study center staff should monitor subjects who are taking concomitant medications that are metabolized by CYP2C19, CYP2C9, CYP2D6, CYP3A4, CYP1A2, or by P-glycoprotein with special care.

6.2.9. Pharmacokinetics Assessments

To assess PK parameters, blood draws will be obtained at Visit 3, Visit 5 (fed; Week 4, Day 6) and Visit 6 (fasted; Week 4, Day 7), or the Early Withdrawal Visit. Blood draws for PK values at Visits 5 and 6 will occur as follows:

Fasting/Fed	PK Sample Visits	Time points
Fed: Patients should arrive without food and the morning dose. Site provides a high fat/high calorie food then doses patient	Visit 5 (Week 4, Day 6)	Pre-dose (before meal/morning dose) and 2, 4, 6 hours after the morning dose (but before next dose)
Fasted (2 hours before dose until 2 hours after dose): Patients should arrive without food and the morning dose. Site provides a standard meal 2 hours after dose.	Visit 6 (Week 4, Day 7)	Pre-dose and 2 (before meal), 4, 6 hours after the morning dose (but before next dose)

Whole blood will be obtained in a Vacutainer® tube containing K₂EDTA. Specific sample collection instructions will be provided in a separate pharmacokinetic manual.

7. STUDY PROCEDURES

The assessments and procedures that will be conducted during this study are summarized in [Table 1](#).

7.1. Screening

Potential study subjects will be examined before the start of the study to determine their eligibility for participation. Informed consent must be obtained and signed before initiation of screening activities. The following screening procedures and assessments must be performed within 28 (+/- 5) days before the day of enrollment in the study:

- Obtain written informed consent/assent (if appropriate).
- Review of inclusion and exclusion criteria.
- Review of historic seizure counts based on patient and caregiver reports.
- Dispense seizure and meal diary.
- Record demographics.
- Assessment of past/current AEDs and other concomitant medications.
- Record medical/surgical history.
- Record vital signs (seated blood pressure, pulse rate, temperature, and respiration rate), including height and weight.
- Collect blood samples (clinical chemistry and hematology).
- Perform 12-lead ECG.
- Collect urine sample for urinalysis.
- Urine dipstick pregnancy test (all female subjects of childbearing potential).
- Perform a complete physical examination.
- Perform a complete neurological examination.
- Measure and record height and weight.
- Complete C-SSRS.
- Review AEs.

